11.2.4.2 Evaluation of Best Overall Response

The best overall response is the best response recorded from the start of the treatment until disease progression/recurrence (taking as reference for progressive disease the smallest measurements recorded since the treatment started). The patient's best response assignment will depend on the achievement of both measurement and confirmation criteria. If a response recorded at one scheduled MRI does not persist at the next regular scheduled MRI, the response will still be recorded based on the prior scan, but will be designated as a non-sustained response. If the response is sustained, i.e. still present on the subsequent MRI at least four weeks later, it will be recorded as a sustained response, lasting until the time of tumor progression. Participants without measurable disease may only achieve SD or PD as their best “response.”

11.2.4.3 Duration of Response

Duration of overall response: The duration of overall response is measured from the time measurement criteria are met for CR or PR (whichever is first recorded) until the first date that recurrent or progressive disease is objectively documented (taking as reference for progressive disease the smallest measurements recorded since the treatment started, or death due to any cause. Participants without events reported are censored at the last disease evaluation).

Duration of overall complete response: The duration of overall CR is measured from the time measurement criteria are first met for CR until the first date that progressive disease is objectively documented, or death due to any cause. Participants without events reported are censored at the last disease evaluation.

Duration of stable disease: Stable disease is measured from the start of the treatment until the criteria for progression are met, taking as reference the smallest measurements recorded since the treatment started, including the baseline measurements.

11.2.5 Study Continuation Beyond Initial Progressive Disease

Immunotherapeutic agents such as ipilimumab and nivolumab may produce antitumor

effects by potentiating endogenous cancer-specific immune responses which may manifest as initial worsening of enhancement and edema on MRI or CT scans (i.e. pseudo-progression). In addition, the response patterns seen with immunotherapeutics may extend beyond the typical time course of responses seen with cytotoxic agents, and can manifest a clinical response after an initial increase in tumor burden or even the appearance of new lesions. For these reasons, the immune- related response criteria (irRC) have endorsed continuation of study therapy beyond initial radiographic evidence of progression for clinically stable patients undergoing immune based therapies.

Therefore, the following adaptations will be used to assess response for patients treated on this study:

Potential Pseudo-progression: If radiologic imaging shows initial PD, subjects who are not experiencing significant clinical decline, may be allowed to continue study treatment for up to three months. Patients who have radiographic evidence of further progression after up to three months, or who decline significantly at anytime, will be classified as progressive with the date of disease progression back-dated to the first date that the subject met criteria for progression and such subjects will be discontinued from study therapy. Three months is the most common timeframe for pseudo-progression observed among patients with advanced melanoma or other solid tumors treated with PD-1/PD-L1 immune checkpoint blockade¹⁷.

Among patients on this study with initial radiographic PD, tumor assessment should be repeated regularly in order to confirm PD with the option of continuing treatment as described below while awaiting radiologic confirmation of progression. If repeat imaging shows a stabilization or reduction in the tumor burden compared to the initial scan demonstrating PD, treatment may be continued / resumed. If repeat imaging after up to three months confirms progressive disease, then the date of disease progression will be the first date the subject met criteria for progression and subjects will be discontinued from study therapy. Subjects who have confirmed disease progression will discontinue study medication and enter the follow up/survival phase of the study. In determining whether or not the tumor burden has increased or decreased, investigators should consider all target lesions as well as non-target lesions.

Tumor Enhancement to Define Progression: RANO expanded the previously utilized Macdonald criteria¹⁸ to include the development of “significantly” increased T2 or FLAIR abnormality in the definition of progressive disease because such changes can be a major component defining radiographic progression following therapeutic use of VEGF/VEGFR-targeting therapeutics which are known to elicit potent anti-permeability changes that limit contrast uptake. However, immune based therapies are expected to be associated with inflammatory changes that may include edema. Therefore, our study will define radiographic progressive disease by assessment of enhancing tumor burden only and will not include assessment of T2 or FLAIR changes as outlined in RANO because:

- There is no expectation that immunotherapy agents including PD-1 inhibitors will falsely diminish enhancing tumor burden as has been noted with anti-angiogenic

therapies; and

- Immune based therapies are expected to induce inflammatory responses which may be associated with increased edema and T2/FLAIR changes. Such radiographic finding may inaccurately be interpreted to represent tumor progression (i.e. pseudoprogression).

In subjects who have initial evidence of radiographic PD, it is at the discretion of the treating physician whether to continue a subject on study treatment for up to three months pending confirmation of PD on follow-up imaging. This clinical judgment decision should be based on the subject's overall clinical condition, including performance status, clinical symptoms, and laboratory data. Subjects may receive study treatment while waiting for confirmation of PD if they are not experiencing significant clinical decline and if:

- The subject is believed to demonstrate clinical benefit from the study regimen as determined by the treating physician;
- The subject is adequately tolerating study therapy.

When feasible, study therapy should not be discontinued until radiographic progression is confirmed. This allowance to continue treatment despite initial radiologic progression takes into account the observation that some subjects can have a transient tumor flare in the first few months after the start of immunotherapy, but with subsequent disease response¹⁹. Subjects that are exhibiting significant neurologic decline are not required to have repeat imaging for confirmation of progressive disease.

Participants with progressive radiographic findings are encouraged to undergo surgical intervention in order to delineate pseudo-progression due to inflammation associated with PD-1 blockade from true tumor progression. Participants with histopathologic findings of significant immune infiltrate and evolving gliosis will be allowed to continue study therapy. In contrast, those with clear evidence of progressive tumor by histopathologic evaluation will be defined as progressive and discontinued from study therapy. For such patients, the date of tumor progression will be the first date the participant met radiographic criteria for PD.

11.3 Response Review

All brain MRI scans will be reviewed centrally by the DF/HCC Tumor Imaging Metrics Core (TIMC). CNS response will be assessed centrally using the RANO criteria outlined in Section 12.1.4.

All non-CNS scans will be reviewed centrally by the DF/HCC Tumor Imaging Metrics Core (TIMC). Extracranial response will be assessed centrally using RECIST criteria.

11.4 Other Response Parameters

Cerebrospinal Fluid: Cerebrospinal fluid will collected as part of clinical care.

Leptomeningeal response will be defined as below:

Response	Cytologic	Neurologic	Radiographic
Complete Response	Reversion to (-) CSF cytology (or NA)	Disappearance of all disease related symptoms present prior to therapy (or NA)	Complete disappearance of all detectable radiographic EOD (or NA)
Partial Response	> 50% decrease in malignant CSF cytology	Improvement in neurologic symptoms or no worsening of symptoms	Improvement in radiographic evidence of disease. No new sites of measurable or assessable CNS disease
Stable Disease	Not fulfilling the criteria for CR or PR, but not progressive disease	Not fulfilling the criteria for CR or PR, but not progressive disease	Not fulfilling the criteria for CR, or PR but is not progressive disease
Progressive Disease	> 50% increase in malignant CSF cytology	Development of new neurologic symptoms related to neoplastic meningitis	Increase in radiographic evidence of disease. Appearance of new sites of disease.

Leptomeningeal response will be a secondary outcome.

The immune related Response Criteria (irRC) will also be used in this study to support secondary efficacy endpoints for extracranial lesions. Definitions of the immune-related Response Criteria (irRC) are below and are presented in Appendix B:

- Complete Response (CR): Disappearance of all lesions in two consecutive observations not less than 4 wk apart
- Partial Response (PR): $\geq 50\%$ decrease in tumor burden compared with baseline in two observations at least 4 wk apart
- Stable Disease (SD): 50% decrease in tumor burden compared with baseline cannot be established nor 25% increase compared with nadir
- Progressive Disease (PD): At least 25% increase in tumor burden compared with nadir (at any single time point) in two consecutive observations at least 4 wk apart

Index Lesion	Non-Index Lesion	New Measurable Lesions	New unmeasurable lesions	% change in tumor burden	Overall IR Response
CR	CR	No	No	-100%	irCR
PR	Any	Any	Any	$\geq -50\%$	irPR
PR	Any	Any	Any	$< -50\% \text{ to } < 25\%$	irSD
PR	Any	Any	Any	$\geq +25\%$	irPD
SD	Any	Any	Any	$< -50\% \text{ to } < +25\%$	irSD
SD	Any	Any	Any	$\geq +25\%$	irPD
PD	Any	Any	Any	$\geq +25\%$	irPD

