1.3 Secondary Objectives

1. To describe the toxicity of nivolumab and ipilimumab in brain and leptomeningeal metastases.
2. To estimate the central nervous system response rate (parenchymal brain metastases) of nivolumab and ipilimumab in patients with leptomeningeal disease
3. To estimate the systemic response rate of nivolumab and ipilimumab in patients with brain metastases
4. To estimate leptomeningeal disease response of nivolumab and ipilimumab in patients with leptomeningeal metastases.
5. To estimate the systemic progression free-survival of patients receiving nivolumab and ipilimumab.
6. To estimate the intracranial progression free-survival of patients receiving nivolumab and ipilimumab.

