- 3.1.7. Women of childbearing potential must have a negative serum or urine pregnancy test (minimum sensitivity 25 IU/L or equivalent units of HCG) within 72 hours prior to the start of nivolumab.
- 3.1.8. Women must not be breastfeeding.
- 3.1.9. Men who are sexually active with WOCBP must use any contraceptive method with a failure rate of less than 1% per year. Men receiving nivolumab and who are sexually active with WOCBP will be instructed to adhere to contraception for a period of 31 weeks after the last dose of investigational product. Women who are not of childbearing

potential, ie, who are postmenopausal or surgically sterile as well as azoospermic men do not require contraception

- 3.1.7 Ability to understand and the willingness to sign a written informed consent document.
- 3.1.8 Stable dose of dexamethasone 2 mg or less for 7 days prior to initiation of treatment
- 3.1.9 Carcinomatous meningitis, as defined by positive cytology or biopsy. If CSF cytology is negative, but imaging is consistent with carcinomatous meningitis, patient is eligible.

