11.2.4 Response Criteria

11.2.4.1 Evaluation of Intracranial Lesions

Complete Response (CR): Requires all of the following:

- complete disappearance of all enhancing measurable and nonmeasurable disease sustained for at least 4 weeks
- no new lesions
- stable or decreasing corticosteroids (the steroid dose at the time of the scan evaluation should be no greater than the dose at time of baseline scan)
- stable or improved clinically

Participants with non-measurable disease cannot have a complete response. The best possible response is stable disease.

Partial Response (PR): All of the following criteria must be met:

- Greater than or equal to 50% decrease compared to baseline in the sum of products of perpendicular diameters of all measurable enhancing lesions sustained for at least 4 weeks. In the absence of a confirming scan 4 weeks later, this scan will be considered only stable disease.
- no progression of non-measurable disease.
- no new lesions
- stable or reduced corticosteroid dose (the steroid dose at the time of the scan evaluation should be no greater than the dose at time of baseline scan)
- stable or improved clinically

Progressive Disease (PD): At least one of the following must be true:

- $\geq 25\%$ increase in the sum of products of all measurable lesions over smallest sum observed (over baseline if no decrease) using the same techniques as baseline
- clear worsening of any nonmeasurable disease*
- appearance of any new enhancing lesion/site
- clear clinical worsening (unless clearly unrelated to this cancer, e.g. seizures, medication side effects, complications of therapy, cerebrovascular events, infection)
- failure to return for evaluation due to death or deteriorating condition

* Progression of non-measurable CNS lesions is defined as follows:

- a lesion initially at baseline $\leq 5\text{mm}$ in diameter that increases to $\geq 10\text{mm}$ in diameter, or
- a lesion initially at baseline 6-9 mm in diameter that increases by at least 5 mm in diameter.

Stable Disease (SD): All of the following criteria must be met:

- Does not qualify for CR, PR or progression
- All measurable and non-measurable sites must be assessed using the same techniques as baseline
- Stable clinically.

A summary of the response criteria is in the below:

	Complete Response	Partial Response	Stable Disease	Progressive Disease
T1-Gd+	None	$\geq 50\%$ decrease	$<50\%$ decrease- $<25\%$ increase	$\geq 25\%$ increase*
New Lesion	None	None	None	Present*

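### The leptomeningeal response table in 11.4 has no corticosteroid condition and no confirmed/unconfirmed label, and unchanged symptoms meet its neurologic PR cell

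*Combined protocol and SAP*

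**What the plan says.** Section 1.3 lists as objective 4: "To estimate leptomeningeal disease response of nivolumab and ipilimumab in patients with leptomeningeal metastases". The only definition of that response is the table in section 11.4, which has cytologic, neurologic and radiographic columns. Section 13.6 counts CR or PR from it and gives a two-sided 90% exact binomial interval.

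- The cytologic CR cell reads "Reversion to (-) CSF cytology (or NA", closing the bracket there. Each of the other two CR cells also allows NA. The PR cells do not.
- The neurologic PR cell reads "Improvement in neurologic symptoms or no worsening of symptoms".
- Nothing in the table, or in 13.6, mentions corticosteroids, a repeat assessment, a minimum duration, or how the three columns combine.

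The criteria for parenchymal brain lesions in section 11.2.4.1 are stricter. CR needs "complete disappearance of all enhancing measurable and nonmeasurable disease sustained for at least 4 weeks". For PR, "In the absence of a confirming scan 4 weeks later, this scan will be considered only stable disease". Both also require that "the steroid dose at the time of the scan evaluation should be no greater than the dose at time of baseline scan". Section 11.2.4.2 then handles a response that does not persist differently: "the response will still be recorded based on the prior scan, but will be designated as a non-sustained response".

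On steroids, the dexamethasone criterion in 3.1 (numbered 3.1.8) and exclusion 3.2.4 apply only before treatment starts. Section 6 gives advice for participants who need more than 4 weeks of corticosteroids for an adverse event. It also allows dosing interruptions for prolonged tapers and says tumor assessments continue meanwhile.

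**The concern.** This is the only response endpoint aimed at the disease that defines the trial, and the trial has a single arm, so no control rate would expose an inflated figure. The protocol already treats steroid exposure above baseline as a reason not to credit a brain-lesion response, yet the leptomeningeal table is silent on it. A participant assessed during a steroid course given for an immune-related event could show better symptoms or less enhancement and be credited with leptomeningeal response. The same participant's brain lesions could not be credited. The neurologic PR cell goes further and credits a participant whose symptoms have not changed. A single negative tap is also accepted without any label showing whether the next one agreed. Each error runs upward. With 18 patients, one wrongly credited response moves the rate by 1/18 = 5.6 percentage points.

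**Working it through.** **1. The plan's own figure.** Section 13.6 states a maximum 90% interval width of 0.42 for 18 patients. The exact (Clopper-Pearson) interval is widest at 9 of 18: 0.291 to 0.709, width 0.4176. The figure reproduces. The defect concerns bias, so this width neither reveals it nor changes when it is corrected.

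**2. The two sets of criteria side by side.**

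| Condition for CR or PR | Brain lesions (11.2.4) | Leptomeningeal disease (11.4, 13.6) |
|---|---|---|
| Steroid dose no greater than at baseline | Required | Not mentioned |
| Persistence | 4 weeks in 11.2.4.1; 11.2.4.2 records a response that does not persist but labels it non-sustained | No requirement and no label |
| Clinical state | Stable or improved, as an added condition beside a measured decrease | No worsening is enough to fill the neurologic PR cell |

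**3. The neurologic column taken alone.** PR covers improvement or no worsening. PD requires new symptoms. Stable disease is what remains: existing symptoms worse, but none new. A participant with unchanged symptoms is therefore PR in this column, not stable. This follows from the table and needs no assumption.

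**4. How an error in one column becomes a response.** The outcome depends on the unstated combining rule.

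- If one column suffices, unchanged symptoms alone give PR, as does a steroid-related improvement in symptoms or imaging.
- If all columns must agree, CR on one negative tap is possible where the neurologic and radiographic cells are met or NA. PR also needs a fall of more than 50% in malignant cytology and radiographic improvement. Steroid effects could then supply the neurologic and radiographic columns but not, on their own, the cytologic one.

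**5. Illustration of repeated taps.** The documents give no false-negative rate, so let f be an assumed rate per tap in a participant whose disease is unchanged, with taps independent. The induction calendar gives on-treatment taps at weeks 4, 7 and 10 (k = 3). The calendar for non-small cell lung and head and neck cancer gives weeks 5 and 9 within the first 12 weeks (k = 2).

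At least one negative: 1 − (1 − f)^k. Two consecutive negatives: 2f² − f³ for k = 3, and f² for k = 2.

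| f | k = 3, at least one | k = 3, two in a row | k = 2, at least one | k = 2, two in a row |
|---|---|---|---|---|
| 0.1 | 27% | 1.9% | 19% | 1% |
| 0.2 | 49% | 7.2% | 36% | 4% |
| 0.3 | 66% | 15% | 51% | 9% |
| 0.5 | 88% | 38% | 75% | 25% |

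For example, at f = 0.1 and k = 3: 1 − 0.9³ = 0.271, and 2(0.01) − 0.001 = 0.019. These are chances of negative taps, not of a leptomeningeal response. Correlated results, such as persistently low shedding of cells, would make a second tap less protective than shown.

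**The case against.** The case against is strong in several places.

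- A reader might take the negative-tap percentages as the expected false response rate. The documents do not support that. Response has three columns, and section 11.1.1 requires re-evaluation with both scans and cytology. A participant with visible, unchanged imaging does not meet the radiographic PR or CR cell. Neither f nor independence has a source in the plan.
- A reader might infer that participants who enter under "If CSF cytology is negative, but imaging is consistent with carcinomatous meningitis, patient is eligible" would be scored as cytologic responders. Section 11.1.1 restricts evaluability for target response to positive baseline cytology, so the risk is an apparent reversion during the study.
- A reader might infer that confirmation is a uniform rule from which 11.4 alone departs. It is not. Section 11.2.4.2 keeps non-sustained brain responses, and the RECIST table in 11.1.4.4 limits its confirmation requirement to trials with response as the primary endpoint. The irRC in 11.4 do require two observations at least 4 weeks apart, but only for extracranial lesions.
- Section 6 does not predict long steroid courses. It says what to consider if they are needed.
- Section 13.2 puts median survival at about 2–4 months. Turning every unconfirmed response into stable disease would make non-responders of participants who die or miss a tap, and could replace upward bias with downward bias.
- No test or go/no-go rule uses this endpoint.

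All of this stands, and it limits the size of the point and the form of the remedy. It does not supply the missing steroid condition, the missing label or a reason to call unchanged symptoms a partial response. Central review under 11.3 covers scans, not symptoms or cytology.

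**Conclusion.** The point holds as a gap in an endpoint definition. As written, 11.4 allows steroid-related improvement, unchanged symptoms, or one negative tap with the other columns met or NA to contribute to, and under some readings to be sufficient for, a leptomeningeal response. The steroid contrast with 11.2.4.1 is the clearest part. The confirmation contrast is weaker because the brain-lesion text is itself divided between downgrading and labelling. The direction of bias is upward. Its size cannot be derived from the documents, and the only firm figure is 5.6 points per misclassified patient among 18. It affects a descriptive secondary rate and its comparability with the intracranial rate. Three-month survival and the two-stage decision rule are untouched. The correction is worth making before analysis because it is cheap.

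**What to change.** Amend section 11.4 as follows.

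1. Leptomeningeal CR or PR requires a corticosteroid dose at assessment no greater than at baseline, as in 11.2.4.1, except for physiologic replacement. Name the date that defines the baseline dose, since section 10 allows the baseline scan and the qualifying CSF to be taken at different times.
2. Unchanged or absent symptoms support PR only when the cytologic or radiographic column shows improvement. Worded this way, participants without symptoms can still reach PR. The rule for combining columns has to be stated for this to take effect.
3. Report each response as confirmed (present on the next scheduled CSF sample or assessment) or as non-sustained/unconfirmed, following 11.2.4.2, and give both rates in 13.6. Do not reclassify every unconfirmed response as stable disease.

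The cost is wording in 11.4 and 13.6. CSF is already scheduled every 3 to 4 weeks and concurrent medications are already on the study calendar; steroid dose at each leptomeningeal assessment must be extractable. The downside is a somewhat lower reported rate, and some early deaths or missed taps will leave responses unconfirmed. Showing both rates makes that visible.
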